14.0 Comparison of usual care and study procedures

14.1 Clients visiting Vivent Health may choose not to participate in the study. There is no alternative to participating if they choose not to participate.

14.2 Regardless of study participation, clients at Vivent Health can continue to receive their usual prevention services from Vivent Health, including but not limited to obtaining sterile injecting equipment and other supplies, referrals, and hepatitis C and HIV testing.

14.3 Study participants are provided with some overlapping information about overdose prevention, COVID-19, and health and social services via the Thrive4Life Connect smartphone application that could be obtained from staff working at Vivent Health. Specifically, the Thrive4Life Connect app contains a resources section with flyers and information on these topics, which are also available at Vivent Health.

14.4 Research participation will not affect access to Vivent Health prevention services or any other care or treatment the participant is involved in.

15.0 Withdrawal of Participants

15.1 The Thrive4Life Connect application allows participants to share their views, opinions, photos and personal experiences. However, participants are prohibited to post content on the Thrive4Life Connect site that promotes racism, bigotry, hatred, nudity, or physical harm of any kind against any group or individual. If participants use the application in an inappropriate manner, research staff will delete the inappropriate messages and follow up with them. If the behavior continues, research staff may withdraw participants from the study.

PROTOCOL TITLE: iThrive WI – A smartphone intervention for overdose and risk and COVID-19 among people who use drugs

Participants expressing severe emotional or mental distress (e.g., by communicating thoughts of harm to self or others) may also be withdrawn from the study by study staff (or by their own choice). Withdrawal decisions will be made jointly by the research team and lead researchers.

If a participant is incarcerated, no research activities would occur during the time of incarceration. Participants can contact the study team when they are released to discuss participating in the study. If participants are under criminal justice supervision and are prohibited from using internet-enabled devices, it is their responsibility to ensure that their study participation is allowable under the terms of their supervision.

15.2 Orderly termination will involve informing the participant that they are being withdrawn from the study. The study team will then have the ability to remove access from the study activities on the Thrive4Life Connect application and to deactivate the data plan on their study-provided smartphone.

15.3 See 15.2.

Participants are able to end their participation in the study at any time. Participants who do not complete the 12-week intervention will still be eligible to complete the 3-month and 6-month paid study surveys. This situation will be considered a partial withdrawal. These partial withdrawals will be reported in the same way, in continuing reviews, as withdrawals. Data may continue to be collected if partially withdrawn participants begin using the Thrive4Life Connect app again and if they decide to still complete the 3-month and 6-month surveys. If participants partially withdraw and their phone service is turned off, they can contact the study team to discuss participation and turning the service back on. All surveys can be completed without phone service using Wi-Fi.

- Other software option that will be stored on departmental server. *Specify the department:* School of Medicine and Public Health HIPAA-compliant servers
- Locked filing cabinet or drawer inside a locked room. *Specify the building:* School of Medicine and Public Health WARF building
- Other (describe): HIPAA-compliant Vivent Health Microsoft Teams – Information about study survey completion dates will be collected for each participant. This information will be used to inform whether a specific participant is eligible to pick up their compensation for each survey. Vivent Health personnel will also update the Microsoft Teams to reflect when a participant has picked up their compensation.
- Portable devices will be used to access secure web-based data collection sites such as ICTR's REDCap. No data will be stored locally on the device.

16.2 Management of Identifiers:

- Identifiers will be destroyed at study closure or at the time of publication.

16.3 Data will be stored on the Thrive4Life Connect mobile application platform, HIPAA-compliant servers at the UW School of Medicine and Public Health , DOM REDCap, and HIPAA-compliant Vivent Health Microsoft Teams, as described above. Because data are collected electronically, separate data storage for each study site is not necessary and will not be used.

The Thrive4Life Connect app was developed based on the UW-Madison Addiction-Comprehensive Health Enhancement Support System (A-CHESS) platform, which has been used in several prior addiction-related studies. Any data stored on a participant's device are stored in an encrypted file and only accessible by that participant, i.e. participants don't have any other participant's data on their phone. These data are only collected after the participant has signed into their account and are removed when the participant signs out of the Thrive4Life Connect A-CHESS based

PROTOCOL TITLE: iThrive WI – A smartphone intervention for overdose and risk and COVID-19 among people who use drugs

application. Any data transferred to and from UW-Madison servers are done through an encrypted connection.

Thrive4life Connect utilization data that will be used for study analyses of Thrive4Life Connect app utilization are stored on HIPAA Compliant servers housed at the UW-Madison Division of Information Technology (DoIT). DoIT partners with the UW-Madison Office of Cybersecurity to ensure that our infrastructure meets the necessary security controls.

16.4 Data including identifiers from this study will only be shared with members of the study team at UW-Madison and Vivent Health.

17.0 Provisions to Protect the Privacy Interests of Participants

17.1 Steps to protect participants' privacy interests:

- Procedures will be performed in a private area where others cannot see the procedures being performed or overhear the conversation between subjects and researchers.
- All members of the study team are up to date on their institutional HIPAA training.

We have strict rules to protect participant personal information and protected health information (PHI). We will limit who has access to participant health information, names, addresses, phone numbers, and other identifiable information. We will also store this information securely. We may publish and present what we learn from this study, but none of this information will identify participants directly without permission. Study participants will also be protected by a Certificate of Confidentiality.

Federal or state laws may permit or require us to show information to university or government officials and to study sponsors responsible for monitoring this study. There are some situations when we will not keep information confidential. We will report information about participants to the appropriate authorities in the following circumstances:

- If they tell us they are planning to harm themselves or another person.
- If they tell us something that causes us to believe that a child or vulnerable adult is being abused

17.2 This study involves collecting sensitive information about drug and alcohol use on surveys in the Thrive4Life Connect app. The primary objective of this study is to test a novel mobile health intervention to reduce overdose risk and support vaccine uptake with people who inject drugs in Wisconsin. To assess the effectiveness of this study

PROTOCOL TITLE: iThrive WI – A smartphone intervention for overdose and risk and COVID-19 among people who use drugs

and fulfill the study goals, the collection and analysis of this sensitive information is necessary.

17.3 Participants will be able to stop their participation at any time throughout the study. Additionally, participants can refuse to answer any survey question(s) that may make them uncomfortable. Throughout the study, participants will also be encouraged to reach out to the study team if they have any questions. Based on a participant's survey answers, they will also be connected with resources that are specific to their situation. We also obtained a Certificate of Confidentiality for the study and will explain what this means to participants during the informed consent process.

18.0 Sharing of Results

18.1 Results from this study will not be shared directly with participants or others. Individual results will not be reported in participants' health records.

18.2 We will only share results in an aggregate format, and we will not share any data that could be used to identify participants. We will only report summary data to individuals outside the study team. We expect to publish manuscripts based on information gathered in this study, but no participants will be identified in these shared results.

19.0 Data and Specimen Banking

19.1 Data from this pilot study will be banked for future use. Data banking will not be optional. Deidentified data from this study, specifically Thrive4Life Connect survey answers, will be stored on HIPAA compliant secure servers at the UW-Madison School of Medicine and Public Health.

Banked data will be stored indefinitely, but study ID numbers will be removed from data before banking. Banking will occur after all publications for this study are completed and published or after 7 years (whichever comes first).

Members at UW-Madison that can see and use participant information:

- Members of our research team
- Offices and committees responsible for the funding and oversight of research

19.2 Data to be stored:

We will collect the following data directly from participants using survey responses in the Thrive4Life Connect app:

- Overdose and COVID-19 health-related goals

PROTOCOL TITLE: iThrive WI – A smartphone intervention for overdose and risk and COVID-19 among people who use drugs

- Substance use and overdose risk, knowledge, attitudes, beliefs, concerns, and behaviors
 - Safer behaviors
 - Risk behaviors
- Overdose perspectives and experiences
- COVID-19 knowledge, attitudes, beliefs, concerns, and behaviors
- General attitudes towards vaccines
- COVID-19 vaccination status and history
- Event-level information about the most recent time a participant used drugs
 - Daily check-ins (ecological momentary assessments)
- Survey completion dates
- Demographic information
- Frequency and distribution of questions where participants chose “Prefer not to answer”

Supplementary data may also be collected indirectly from participants based on their activity in the Thrive4Life Connect app:

- Discussion board participation
- In-app private messaging with study staff
- Viewing of in-app resources
- Usage of “My Motivation” and “My Gratitude”

Information from participants collected from databases like the Wisconsin Immunization Registry, Medicaid, and Wisconsin hospitalization, emergency medical services, and infectious disease surveillance registries.

All data will be deidentified prior to banking.

19.3 To comply with some academic journal requirements, we anticipate needing a procedure to make data available to interested colleagues. Written requests to release deidentified data or specimens may be made to the lead researchers by email. Requests must specify the specific data requested. The lead researcher would then supply a deidentified dataset based on the data requested. No PHI will be shared in a requested dataset.

19.4 Participants will not be able to withdraw their banked data for future research use. All data will be fully anonymized prior to banking. If a participant decides to withdraw from the study, no additional data will be collected from them after that point.

20.0 Study Analysis

PROTOCOL TITLE: iThrive WI – A smartphone intervention for overdose and risk and COVID-19 among people who use drugs

20.1 Primary Outcome Null hypothesis (feasibility): the study is feasible based on intervention content completion rates of at least 50%. Alternative hypothesis: fewer than 50% of intervention content is completed.

Secondary outcome null hypothesis #1 (preliminary effectiveness of overdose content): there is no difference in the number of days endorsing overdose risk behaviors per month at baseline vs. 3 months and baseline vs. 6 months. Alternative hypothesis: the frequency of overdose risk behaviors decreased from baseline to 3 months, and baseline to 6 months.

Secondary outcome null hypothesis #2 (preliminary effectiveness of COVID-19 content): there is no difference in proportion of participants who have been vaccinated against COVID-19 at baseline vs. 3 months and baseline vs. 6 months. Alternative hypothesis: the proportion vaccinated will increase from baseline to 3 months, and baseline to 6 months.

20.2 As a pilot feasibility study, the number of participants (n=60) reflects the maximum allowable participants in our budget and study timeframe. A formal sample size calculation was not done.

20.1 All participants who enroll in the study will be included in each analysis.

20.4 The average and variation in percentage of completed intervention modules and in the percentage completing each weekly intervention module over 12 weeks will be calculated and examined descriptively.

We will examine changes in the frequency of endorsing overdose risk behaviors and COVID-19 vaccination based on a descriptive analysis of the baseline, 3 month and 6 month surveys. We may also test for differences using appropriate statistical tests, including paired t-tests, McNemar's test, and models appropriate for count outcomes and repeated measures (Poisson or Negative Binomial Generalized Estimating Equations). As a pilot study, we expect that most analyses will be descriptive rather than inferential in nature.

20.5 We will examine weekly survey and intervention module completion rates. There are no stopping rules for efficacy or safety in this study.

20.6 As a pilot feasibility study, we will examine missingness and survey completion as primary outcomes to assess engagement with intervention content and study feasibility. We may impute or use simple techniques such as last observed carried forward in analyses. We will track reported reasons for missing data such as loss of study phone, incarceration, withdrawal, etc.

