4.0 Number of Participants

4.1 This study will include 60 participants in total across 3 Vivent Health syringe services locations in Wisconsin – Milwaukee, Appleton, and Eau Claire.

- Milwaukee: 30 participants
- Appleton: 15 participants
- Eau Claire: 15 participants

4.2 In a prior longitudinal study with Vivent Health (WI Rural Opioid Initiative - Intervention phase), we have experienced up to 50% attrition at 3 months and 6 months. Because of this, we may enroll up to 90 participants in this study.

4.3 Enrolled participants are individuals who complete the baseline survey. Participants who leave the study early (i.e., before completing the 3-month study assessment) may be replaced.

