13.2 Schedule of Procedures and Study Outline

This study will involve required and optional procedures.

Required activities include:

- Thrive4Life Connect
- Surveys
 - Baseline survey
 - 12 weekly check-in intervention surveys about overdose prevention
 - 3-month survey
 - 9 daily check-in surveys
 - 6-month survey
- Surveys will collect information about: Name, age, gender identity, ZIP code, race and ethnicity, education, marital status, alcohol and drug use, types of health care received, mental health, and other related items.
- Private messaging: Study staff will send participants messages in Thrive4Life Connect to remind participants about when surveys open, send personalized resources, and answer any questions.

PROTOCOL TITLE: iThrive WI – A smartphone intervention for overdose and risk and COVID-19 among people who use drugs

- Data linkage to databases like the Wisconsin Immunization Registry, Medicaid, and Wisconsin hospitalization, emergency medical services, and infectious disease surveillance registries.

Optional activities include:

- Interactive modules about COVID-19 vaccines
- Sharing thoughts on discussion boards and private messaging others
- Engaging with online and local resources in the app
- Logs for motivation and thoughts of gratitude
- Using UW-Madison study team contact information.

See the study timeline/flowchart below for a detailed overview of when various activities will occur.

PROTOCOL TITLE: iThrive WI – A smartphone intervention for overdose and risk and COVID-19 among people who use drugs

13.3 After recruitment, study participants will be involved in the following procedures: eligibility screening, informed consent and study enrollment, baseline surveys, 12-week intervention session, 3-month follow-up surveys, and 6-month follow-up surveys.

PROTOCOL TITLE: iThrive WI – A smartphone intervention for overdose and risk and COVID-19 among people who use drugs

Recruitment, screening for eligibility, and informed consent and enrollment will follow the procedures previously described (See “Recruitment” and “Informed Consent” sections).

During the initial enrollment appointment and after providing informed consent, participants will complete the baseline survey and first of three daily check-ins (ecological momentary assessments).

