We may use identifiable information from participants to link their information to databases like the Wisconsin Immunization Registry, Medicaid enrollment and claims data managed by the UW-Institute for Research on Poverty (IRP), and Wisconsin hospitalization data

PROTOCOL TITLE: iThrive WI – A smartphone intervention for overdose and risk and COVID-19 among people who use drugs

from the Wisconsin Hospital Association Info Center, emergency medical services from the Wisconsin Ambulance Run Data System, and infectious disease surveillance registries capturing COVID-19, hepatitis C, and HIV infections. The purpose of this linkage is to understand how people who inject drugs use health care resources as well as to gather outcome data such as COVID-19 infection or vaccination status, overdose events, and substance use or other treatment utilization. To accomplish this, we will link multiple datasets using individual identifiers (name, date of birth, address, sex, race, phone number).

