- Overdose and COVID-19 health-related goals
- Substance use and overdose risk, knowledge, attitudes, beliefs, concerns, and behaviors
 - Safer behaviors
 - Risk behaviors
- Overdose perspectives and experiences
- COVID-19 knowledge, attitudes, beliefs, concerns, and behaviors
- General attitudes towards vaccines
- COVID-19 vaccination status and history
- Event-level information about the most recent time a participant used drugs
 - Daily check-ins (ecological momentary assessments)
- Survey completion dates

Source Records:

- Data from outside institutions or organizations (specify: Wisconsin Department of Health Services and Medicaid, registries described above)
- Other (specify: A-CHESS Thrive4Life Connect mobile app utilization data)

Supplementary data will be collected indirectly from participants based on their activity in the Thrive4Life Connect app:

- Discussion board participation
- In-app private messaging with study staff
- Viewing of in-app resources
- Usage of “My Motivation” and “My Gratitude”
“My Motivation” and “My Gratitude” are optional activities available in the Thrive4Life Connect app.

“My Motivation” prompts participants with the following, “Stay motivated by keeping a list of why you want to stay well - and watch your list grow!” This area then provides

PROTOCOL TITLE: iThrive WI – A smartphone intervention for overdose and risk and COVID-19 among people who use drugs

participants with an opportunity to curate a personal log of things (text or pictures) that motivate them to meet their goals.

“My Gratitude” prompts participants with the following, “Awareness and appreciation of things you’re thankful for may help brighten your day. What are you grateful for?” Participants can then curate a personal list of things (text only) that they are grateful for in “My Gratitude.”

13.5 The Thrive4Life Connect mobile application does not require FDA regulation, as per consultation with the Administrative Director of the FDA Regulated Research Oversight Program.

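### Section 20.4 takes the COVID-19 vaccination outcome from surveys alone and gives no role to the registry linkage planned in Sections 13.2 and 13.3

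*Combined protocol and SAP*

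**What the plan says.** - **Hypothesis (20.1).** The second secondary null hypothesis is that "there is no difference in proportion of participants who have been vaccinated against COVID-19 at baseline vs. 3 months and baseline vs. 6 months". It names no data source.
- **Analysis (20.4).** Change will be examined in "COVID-19 vaccination based on a descriptive analysis of the baseline, 3 month and 6 month surveys". No other source is named anywhere in Section 20.
- **Survey content (13.4).** The items collected from participants through the app include "COVID-19 vaccination status and history". Section 17.3 lets participants decline any item.
- **Linkage (13.2, 13.3).** The required activities in 13.2 include "Data linkage to databases like the Wisconsin Immunization Registry, Medicaid, and Wisconsin hospitalization" data. Section 13.3 says the linkage is partly to "gather outcome data such as COVID-19 infection or vaccination status, overdose events, and substance use or other treatment utilization", but its operative sentence is permissive: "We may use identifiable information from participants to link their information to databases like the Wisconsin Immunization Registry". The request to the state data governance board is to be made once recruitment is complete.
- **Attrition (4.2).** In the prior study with the same partner, "we have experienced up to 50% attrition at 3 months and 6 months".
- **Missing data (Section 20, 20.6).** All enrolled participants are to be in every analysis. Imputation and last observation carried forward are offered as options only.
- **Withdrawal (19.4).** Nothing further is collected from a participant after withdrawal.

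**The concern.** The protocol plans to obtain vaccination status from a source that does not depend on anyone answering a survey, and then leaves that source out of the analysis of the same outcome. Two weaknesses of survey status follow.

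The first is missing status. A person who misses the 3- or 6-month survey has no recorded status there, although the plan says everyone enrolled is analysed. The second is self-report. Participants know they are in the study, and they report through the app that also offers the vaccine content. With no control group, a change in reporting cannot be told apart from a change in vaccination.

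There is also no rule for which source counts if registry data do arrive and disagree with the survey. That choice would be made after both sets of results are visible. At stake is how the preliminary effectiveness of the COVID-19 content is read.

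**Working it through.** The plan gives no sample size calculation, effect size or vaccination rate, so there is no figure to reproduce. The inputs from the documents are 60 participants (4.1) and attrition of up to 50% (4.2). All other inputs below are assumptions. The documents give 50% vaccine hesitancy in the team's survey (2.3), not a vaccination rate. Half unvaccinated at baseline is used as a stand-in.

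1. **Missing status.** 60 × 0.50 = 30 participants without survey status at a follow-up. If 90 are enrolled (4.2), the figure is 45.

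2. **What that leaves unknown.** With x of the 30 responders vaccinated, the follow-up proportion among 60 lies between x/60 and (x + 30)/60, a width of 30/60 = 50 points. Prior vaccination cannot be undone. If half of the 30 lost were already vaccinated at baseline, only 15 are uncertain, and the width is 15/60 = 25 points.

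3. **Precision of a proportion near 0.5.** The 95% half-width is 1.96 × √(0.25/n).
   - n = 30: 17.9 points.
   - n = 60: 12.7 points. This requires every participant to be matched and none to have withdrawn.

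4. **Last observation carried forward.** A missing participant cannot change status, so the change shown = true change × (1 − loss). With 50% unvaccinated and 20% of them vaccinated by follow-up, whether lost or not, the true change is 0.50 × 0.20 = 10 points. At 50% loss it shows as 10 × 0.5 = 5 points. Over 40–60% unvaccinated and 10–30% uptake, true changes of 4–18 points show as 2–9. This error is **towards no change**.

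5. **Self-report error.** Let b be the true proportion vaccinated, Se sensitivity and Sp specificity. The reported proportion is b × Se + (1 − b) × (1 − Sp).
   - Same accuracy at both visits (Se = Sp = 0.95): a true 10 points shows as 10 × (0.95 + 0.95 − 1) = 9.0, and a true zero shows as zero.
   - Specificity falling from 0.95 at baseline to 0.90, 0.85 or 0.80 at follow-up, with b = 0.5 and no new doses: 0.5 × 0.05, 0.5 × 0.10 or 0.5 × 0.15 gives a spurious rise of 2.5, 5.0 or 7.5 points.
   - The error is **upward** only if over-reporting grows after baseline.

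6. **Selective response.** Take 30 vaccinated and 30 unvaccinated, no new doses, and response of 60% and 40%. Responders are 18 and 12.
   - Unpaired: 18/30 = 60% at follow-up against 30/60 = 50% at baseline, a spurious 10 points.
   - Paired, on the same 30 people: 60% against 60%, no change.

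7. **The same test applied to the registry.** If it records a constant share c of doses, it shows c times the true change. The documents do not give c, the match rate, or a statement that the extract carries dose dates.

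**The case against.** The strongest reply is that the registry is not in hand. Linkage is worded as optional in 13.3. It needs board approval, a data use agreement and institutional signature, all after recruitment, which may take 8 months (12.1) or up to a year (25.1). Analyses are expected to finish by August 31, 2024 (12.1). Making the outcome depend wholly on unapproved data would be unwise. This stands, and it is why the fix is conditional and keeps the survey analysis as fallback.

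Second, the team has not overlooked the registry. Section 13.3 names vaccination status as a purpose of linkage, and 20.4 does not exclude it. This also stands. The defect is that the two sections are not joined.

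Third, exposure is lighter than 12 weeks of vaccine promotion. The COVID-19 modules (13.2) and COVID-19 goals (13.3) are optional. This weakens the case for desirability bias without removing it, because the weekly check-ins still cover motivation about vaccination status.

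Fourth, 19.4 may bar registry look-up for those who withdraw. That limits the gain. However, missing a survey is not in itself withdrawal, and Section 15 lets people who stop the intervention still supply survey data.

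A reader might infer that the survey result must overstate uptake, or that the registry would be free of error. The documents support neither. The plausible errors run in opposite directions, the 10-point selection example vanishes under pairing (20.4 names McNemar's test as an option), and registry completeness is not stated.

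**Conclusion.** The point holds as an omission in the analysis plan. Section 20.4 uses surveys alone for a named secondary outcome, while 13.2 and 13.3 plan a second source that does not rely on survey response.

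The one size that rests on the documents is that up to 30 of 60 could lack survey status at a follow-up. This carries the prior study's upper attrition figure over to this one. The bias in the estimated change cannot be signed. The illustrations run from a true 10 points shown as 5 to a true zero shown as a rise of 2.5 to 7.5, all on assumed uptake and reporting accuracy.

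The gain from the registry depends on approval in time, the match rate, recording completeness and usable dates, none of which the documents give. Even perfect dose data could not attribute change to the app without a comparator. The change is therefore worth making but modest, and the primary feasibility conclusion does not depend on it.

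**What to change.** Add a short paragraph to 20.4:

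- If linkage is approved and completed, report vaccination by the baseline, 3-month and 6-month dates from registry records. Do so for all linked participants, including those who missed surveys but did not withdraw.
- State, consistently with 19.4, whether registry records may be used for those who withdrew.
- Use self-report for unmatched participants and as a sensitivity analysis. Tabulate agreement between the two sources at each time point, and fix in advance how disagreements are resolved.
- If linkage is not obtained in time, the paired survey analysis is the fallback.

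Also reconcile the required status of linkage in 13.2 with the permissive wording in 13.3.

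The cost is a paragraph and no new procedure for participants. The downside is that registry data come late and may miss unrecorded doses, which is why self-report stays. The linkage must also be done before identifiers are destroyed at study closure or publication (16.2).

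### Section 20.6 permits, without requiring, last observation carried forward; used for risk-behavior days, it would scale the 3-month mean change by the fraction observed and carry 3-month values into month 6

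*Combined protocol and SAP*

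**What the plan says.** Section 20.6 states: "We may impute or use simple techniques such as last observed carried forward in analyses". Imputation is mentioned without a model. The section does not say which outcomes it covers, and it names neither a main method nor a sensitivity analysis. It does plan to record why data are missing, and it counts missingness among the feasibility outcomes.

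The paragraph numbered 20.1 for the second time sets the analysis population: "All participants who enroll in the study will be included in each analysis". Section 4.3 defines the term: "Enrolled participants are individuals who complete the baseline survey". Everyone analysed therefore has a baseline survey, although single items may be skipped.

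Secondary outcome 1 in section 20.1 compares "the number of days endorsing overdose risk behaviors per month at baseline vs. 3 months and baseline vs. 6 months". As optional analyses, section 20.4 lists the paired t-test, McNemar's test and "models appropriate for count outcomes and repeated measures (Poisson or Negative Binomial Generalized Estimating Equations", with no working correlation given. It adds that "we expect that most analyses will be descriptive rather than inferential in nature".

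On expected loss, section 4.2 reports from a prior study with the same partner that "we have experienced up to 50% attrition at 3 months and 6 months", and for that reason "we may enroll up to 90 participants in this study". Section 3.3 says the 6-month survey is there to show whether 3-month changes lasted. Under section 15, people who stop the intervention may still complete both follow-up surveys.

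**The concern.** The plan wants every enrolled person in every analysis and allows for substantial loss, so some rule must deal with absent follow-up values. The only concrete rule offered is LOCF. At 3 months the sole earlier survey is baseline, so LOCF records no change for everyone who was lost. At 6 months it copies the 3-month value for anyone lost in between, so whatever was seen at 3 months, whether better, worse or unchanged, is recorded as having persisted. Persistence is exactly what the 6-month survey is meant to find out.

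At stake is the reported change in secondary outcome 1, which the plan labels preliminary effectiveness. Because the analysis is mainly descriptive, the mean is itself the result, and part of it would come from the filling rule.

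**Working it through.** **Inputs.** From the documents: three surveys (baseline, 3 and 6 months), all enrolled analysed, 60 planned or up to 90 enrolled, and loss of up to 50% in a prior study. The plan has no effect size, SD or power figure to reproduce; section 20.2 says no formal sample size calculation was made. Assumed for illustration: completers' mean change D = −4 days and SD of change 8, unless stated otherwise.

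**1. Mean at 3 months.** With fraction m missing, the LOCF mean is (1 − m) × D + m × 0 = (1 − m) × D. The ratio does not depend on sample size, SD or D.

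| Missing at 3 months | LOCF ÷ completers' mean | LOCF mean if D = −4 |
|---|---|---|
| 20% | 0.80 | −3.2 |
| one third | 0.67 | −2.7 |
| 50% | 0.50 | −2.0 |

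**2. Direction of bias.** If dropouts truly changed by d, the true mean is (1 − m) × D + m × d. With m = one third, LOCF gives −2.7 whatever d is. The truth is −4.0 if d = −4 (LOCF too close to zero), −2.7 if d = 0 (no bias), and −1.3 if d = +4 (LOCF falsely favourable).

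**3. Precision.** Take 60 enrolled and 30 observed.
- Completers: SE = 8/√30 = 1.46.
- LOCF: the sum of squares is 29 × 64 + 30 × 0.5 × 16 = 2,096, so SD = √(2,096/59) = 5.96 and SE = 5.96/√60 = 0.77.

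The filled zeros are counted as if they were observed.

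**4. Month 6.** Take 60 enrolled: 30 seen at both visits, 15 at month 3 only, 15 at neither.
- Effect of −4 at month 3, fully gone by month 6: LOCF = (30 × 0 + 15 × (−4) + 15 × 0)/60 = −1.0; truth 0.
- Effect fully kept: LOCF = (30 × (−4) + 15 × (−4) + 15 × 0)/60 = −3.0; truth −4.

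With 6 lost before month 3 and 6 more by month 6, the fading case gives 6 × (−4)/60 = −0.4. With nobody lost in between it gives 0.

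**5. Simulation on assumed inputs.** Counts from 0 to 30 days, baseline mean 15, SD 9, change −4, SD of change 10 or 6, dropouts like completers. With 60 of 90 observed, the LOCF 95% interval covers the true change in 68% (SD 10) or 35% (SD 6) of trials. Its mean width at SD 10 is 3.5 days, against 5.2 for completers only. With 48 of 60 observed, coverage is 90% or 80%.

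**6. Check of the alternatives.** 90 enrolled, SD of change 10, true change −4, people with high baseline counts lost more often:

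| Method | One third missing | Half missing |
|---|---|---|
| LOCF | −1.6 | −0.8 |
| Completers only | −2.4 | −1.6 |
| Likelihood model | −4.0 | −4.1 |
| GEE, independence, observed data | about −5.0 | about −5.5 |
| Poisson GEE, exchangeable, observed data | −4.1 to −4.2 | −4.1 to −4.2 |

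The likelihood model was checked with baseline and one follow-up, not all three visits.

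**The case against.** The strongest reply is that the clause is permissive. LOCF stands as an example beside imputation and is not assigned to any outcome. The outcome is secondary, in a small single-arm pilot with no sample size calculation and mostly descriptive aims. All of this stands. A reader might infer that the plan commits to LOCF, or that half the sample will be lost; the text supports neither. The 50% figure is the upper end of experience in a different study, and keeping people who stop the intervention eligible for both surveys may reduce loss.

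A second reply is that LOCF is conservative. That holds only if dropouts improve. If they do not change, LOCF's 3-month mean is right and a missing-at-random model is too favourable: −4.0 against −2.7 with one third missing. If they worsen, or if an effect fades among those lost after 3 months, LOCF flatters the intervention. It does not inflate the 3-month test when nobody changes.

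Third, only the (1 − m) ratio follows from the plan. The day counts, SDs, fading and loss patterns are assumptions; they show possible bias, not its likely size.

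Fourth, a reader might infer that a GEE is unusable without multiple imputation. The check does not show that: the problem arises with an independence working correlation, which the plan does not specify, and largely disappears with an exchangeable one.

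**Conclusion.** The concern holds as a risk left open by section 20.6, not as an error the plan has committed to. If LOCF values enter the analysis of risk-behavior days, the 3-month mean is exactly (1 − fraction missing) times the completers' mean. That rests only on the three-survey schedule, an answered baseline item and the all-enrolled rule. With an assumed completers' change of −4 days and one third missing, the report would read −2.7. At 6 months, those lost after the 3-month survey are recorded as unchanged since then. The direction of bias depends on the dropouts and cannot be settled from the documents; the understated uncertainty does not share that ambiguity.

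The reach is limited. The feasibility primary outcome is unaffected. Vaccination is affected less: carrying status forward gives a lower bound on the proportion vaccinated, and the optional registry linkage in section 13.3 may supply the status. The change is worth making because it is cheap.

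**What to change.** In section 20.6, state that LOCF will not be used for the main estimate of days of risk behavior. In section 20.4, name one main method: a likelihood-based repeated-measures model on all observed baseline, 3-month and 6-month values of all enrolled participants, reporting mean change in days. If the GEE is kept instead, do not fit it to observed data with an independence working correlation; use an exchangeable or unstructured one, or multiply impute first.

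Report observed-case results with the number observed at each visit. Add a short sensitivity table that shifts the missing values by fixed amounts, for example 0, +2, +4, +6 and +8 days, with at least one row placing dropouts above their own baseline. Each row is roughly the main estimate plus fraction missing × shift. For a main estimate of −4 with one third missing, the rows are −4.0, −3.3, −2.7, −2.0 and −1.3; keeping values within the possible range of days moves them slightly.

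If the LOCF view is wanted, show it as a separate labelled row with missing changes set to zero. It should not be read off the +4 row: the two agree only when the main estimate is −4 and dropout is unrelated to baseline. With dropout tied to baseline and one third missing, the +4 row would be −4.03 + 4/3 = −2.7, against −1.6 for LOCF.

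The cost is wording in two sections, one model and one small table, with no new data. Intervals widen: in the simulation with 60 of 90 observed and SD of change 10, about 4.9 days for the model against 3.5 for LOCF. The main estimate assumes data are missing at random, which the shift table probes.
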